# 9.2.1 Palovarotene-exposed Cohort

#### 9.2.1.1 Inclusion Criteria

To be included in the palovarotene-exposed cohort, the participants should fulfil all the following inclusion criteria:

- (1) Paediatric (8 years to less than 18 years of age for girls and 10 years to less than 18 years of age for boys) and adult participants with FOP who have been prescribed palovarotene (prior to and independently of the decision to enrol the patient in the FOPal registry study) by their treating physician, as per local label;
- (2) Signed informed consent as per local regulations must be obtained and maintained. Consent/assent from the participant should be obtained as appropriate before any registry study data collection is conducted. If applicable, parents or legally authorised representatives must give signed informed consent.

#### 9.2.1.2 Exclusion Criteria

Participants will not be included in the palovarotene-exposed cohort if:

- (1) Currently participating in any interventional clinical trial;
- (2) Palovarotene is contraindicated as per the locally approved label (except for pregnant participants who have previously received and discontinued palovarotene at any time during the pregnancy and who will be included for safety follow-up).

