# 8.2.2 Secondary Objectives

For participants with FOP exposed and unexposed to palovarotene:

- To describe the range of motion (ROM) as assessed by the Cumulative Analogue Joint Involvement Scale (CAJIS) for FOP;
- To describe the use of assistive devices and adaptations for daily living;
- To describe the physical function using age-appropriate forms of the Fibrodysplasia Ossificans Progressiva-Physical Function Questionnaire (FOP-PFQ);
- To describe the parameters of lung function (observed and % predicted forced vital capacity (FVC), observed and % predicted forced expiratory volume in one second (FEV1), absolute and % predicted FEV1/FVC ratio, observed and % predicted diffusion capacity of the lung for carbon monoxide (DLCO)) at Baseline and over time;
- To describe the physical and mental health (participants ≥15 years old) and overall quality of life (QoL) (participants <15 years old) using age-appropriate forms of the Patient-Reported Outcomes Measurement Information System (PROMIS) Global Health Scale;
- To describe the flare-up frequency;
- To describe any movement mobility change by body location and annually;
- To describe the number of locations impacted by movement mobility change per participant annually;
- To describe the movement mobility outcomes (change in extra bone growth and change in movement), causes and associated symptoms if preceded by a flare-up event by body location;
- To describe the frequency, severity, outcome and descriptive details of any fractures (including bone fracture and vertebral fractures).
- To describe the incidence of pregnancy.

For participants with FOP exposed to palovarotene who become pregnant while enrolled in FOPal:

- To describe pregnancy characteristics and outcomes;
- To describe pregnancy-related AEs through the first year postpartum;
- To describe birth and developmental outcomes through the infant(s)' first year of life.

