# 9.7 Data Analysis

# 9.7.1 Analyses Population Definitions

For the purposes of analyses, the following populations are defined:

- Enrolled Population including all participants who signed the ICF.
- Safety Exposed Population including all enrolled participants who have taken at least one dose of marketed palovarotene at any time before the signed ICF or during the study; A distinction will be made depending on time of start of marketed palovarotene:
  - Palovarotene prevalent users: participants who received palovarotene before or at the time of ICF signed;
  - Palovarotene incident users: participants who started receiving palovarotene after enrolment in the registry. Two time periods will be defined: Period 1 is from enrolment to last day before the first dose of marketed palovarotene; Period 2 is after the first dose of marketed palovarotene.
- Safety Exposed Paediatric Population including all paediatric participants (8 years to less than 18 years of age for girls and 10 years to less than 18 years of age for boys) from the Safety Exposed Population.
- Safety Unexposed Population including all enrolled participants who never received at least one dose of marketed palovarotene before or during their participation in the registry;
- Safety Unexposed Paediatric Population including all paediatric participants (8 years to less than 18 years of age for girls and 10 years to less than 18 years of age for boys) from the Safety Unexposed Population.

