**PAGE 65 OF 287** 

#### Pregnancy

Confirmation of an absence of pregnancy will be included in the participant data listings using the Safety Exposed Population only.

Incidence of all pregnancies will be summarised for those exposed and unexposed to palovarotene in the Safety Exposed Population. For these analyses, the pregnancy will be considered as exposed to palovarotene if it occurs whilst the participant is using the medicinal product or within 2 days after stopping the product (based on the estimated date of conception).

For participants who become pregnant while enrolled in FOPal, whether exposed or not to palovarotene, pregnancy characteristics and outcomes, pregnancy-related AEs through the first year postpartum, and birth and developmental outcomes through the infant(s)' first year of life will be descriptively summarised by palovarotene exposure status (exposed and unexposed).

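### Participants already pregnant after palovarotene exposure may enrol for safety follow-up, but no planned pregnancy-outcome summary covers them

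*Protocol*

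**What the plan says.** Protocol 9.2.1.2, repeated in the abstract (Section 4), excludes participants for whom palovarotene is contraindicated, "except for pregnant participants who have previously received and discontinued palovarotene at any time during the pregnancy", and adds of these participants: "who will be included for safety follow-up". Section 9.7.1 defines the Safety Exposed Population as enrolled participants who took "at least one dose of marketed palovarotene at any time before the signed ICF or during the study", so these entrants belong to it.

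The outcome objectives in 8.2.2 open with "For participants with FOP exposed to palovarotene who become pregnant while enrolled in FOPal". The objectives at the front of the protocol, the abstract and the endpoints in 9.3.1.2 carry the same limit. The outcome summary in 9.7.3.4 reads: "For participants who become pregnant while enrolled in FOPal, whether exposed or not to palovarotene, pregnancy characteristics and outcomes", followed by pregnancy-related adverse events and infant outcomes, split by exposure status.

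The incidence sentence in 9.7.3.4 is worded differently: "Incidence of all pregnancies will be summarised for those exposed and unexposed to palovarotene in the Safety Exposed Population". It classes a pregnancy as exposed by the estimated conception date, during use or up to 2 days after stopping, without reference to the date of enrolment.

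Collection is mostly wider than the outcome summary. Section 9.3.2.7 follows any pregnant participant through the first year postpartum. Section 11.1.3.1 collects details of all pregnancies from consent, and 11.2.2 requires every pregnancy on the eCRF. Yet another sentence in 11.1.3.1 ties outcome collection to a pregnancy that occurs during enrolment.

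**The concern.** The protocol admits a specific group so that their pregnancies can be followed, then words every outcome objective, endpoint and summary so that the group falls outside. Someone pregnant at consent did not become pregnant during enrolment.

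The stakes are high for so small a group. The protocol describes palovarotene as highly teratogenic (11.1.3.1) and reports no pregnancies in the development programme (7.3.1). One or two exposed pregnancies could be all the registry ever observes. If they entered through the exception, the outcome tables would be empty when produced as written.

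The incidence wording raises a second issue. Women who enter under a rule that applies only to pregnant participants are not at risk of a new pregnancy at entry. If they are counted, the incidence includes cases present by selection.

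**Working it through.** The protocol states no figure for pregnancy incidence, so there is nothing to reproduce. The check has two parts.

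**1. Tracing one participant through the sections.** Take a participant who conceives on palovarotene, stops it during the pregnancy, and then signs consent.

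| Step | Section | Result |
|---|---|---|
| Eligibility | 9.2.1.2 | Admitted by the exception |
| Analysis population | 9.7.1 | Safety Exposed Population (dosed before consent) |
| Follow-up and eCRF | 9.3.2.7, 11.1.3.1, 11.2.2 | Pregnancy and infant followed and recorded |
| Outcome collection sentence | 11.1.3.1 | Not covered (pregnancy did not occur during enrolment) |
| Outcome objectives and endpoints | 8.2.2, 9.3.1.2 | Not covered |
| Outcome summary | 9.7.3.4 | Not covered |
| Incidence summary | 9.7.3.4 | Covered if taken literally; no entry-date rule stated |

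The adverse event tables do not close the gap. Collection (9.3.2.5, 11.2.1) and the treatment-emergent definition (9.7.3.2) both end 30 days after the last dose. This participant stopped before consent, so that window may already have closed, and delivery and infant outcomes will usually fall after it. Abnormal outcomes count as serious adverse events (11.1.3.1), but normal outcomes do not, so those reports give no denominator.

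**2. Size of the possible incidence effect.** Inputs: n = 67, the minimum exposed cohort (9.5, 9.7.2); the pregnancy counts are assumptions. Formula: crude proportion x/n with an exact (Clopper-Pearson) 95% CI.

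| New after enrolment | Present at entry | All pregnancies / 67 | New only / 67 | In outcome summary |
|---|---|---|---|---|
| 0 | 1 | 1/67 = 1.5% (0.04 to 8.0%) | 0% (0 to 5.4%) | 0 of 1 |
| 0 | 2 | 2/67 = 3.0% (0.4 to 10.4%) | 0% (0 to 5.4%) | 0 of 2 |
| 1 | 1 | 2/67 = 3.0% (0.4 to 10.4%) | 1.5% (0.04 to 8.0%) | 1 of 2 |

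Each pregnancy present at entry adds 1/67 = 1.5 points. If only females form the denominator the step is larger. Assuming about half of 67 are female, say 34, it is 1/34 = 2.9 points. The protocol gives neither the number of females nor the denominator.

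**The case against.** The strongest reply is that little is lost. Sections 9.3.2.7, 11.1.3.1 and 11.2.2 follow and record these pregnancies, and 9.2.8 keeps participants who stop because of pregnancy under follow-up. The design summary in 9.1 promises pregnancy outcomes without restriction. Drug exposure during pregnancy is a Special Situation (11.1.3), and Special Situations are tabulated in the Safety Exposed Population (9.7.3.2). All of this stands. A reader might infer that the evidence on these pregnancies is lost to the registry, and the documents do not support that. What remains is that no objective, endpoint or outcome summary uses the data, and that the Special Situation route is partial because it shares the 30-day cut-off.

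On incidence, the endpoint in 9.3.1.2 is simply incidence of pregnancy, which ordinarily means new pregnancies, and time at risk may be left to the SAP. This also stands. A reader might infer that the incidence will be inflated, but no sentence says that pregnancies present at entry are counted. The wording only permits it.

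A reader might also infer that a woman who stopped the day before conceiving is barred by 9.2.1.2 although 9.7.3.4 would class her pregnancy as exposed. The exception does not say how the start of pregnancy is dated, so this cannot be established. At most it concerns the 2-day window, and it carries no weight here beyond a need to reconcile the two wordings.

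**Conclusion.** The scope mismatch holds on the current text. Exposed pregnancies admitted through the exception are collected and followed but belong to no planned outcome objective, endpoint or summary. This does not depend on any assumed count.

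The incidence effect is conditional: it arises only if the reference to all pregnancies is applied literally. It is then 1.5 points per pregnancy at 67 exposed participants, and larger by an unknown amount if only females are the denominator.

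The analysis is secondary and descriptive with no hypothesis testing, so no test or error rate is affected. The change should still be made, because the missing summary concerns what may be the only exposed pregnancies seen.

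**What to change.** - **Outcome population.** In 8.2.2, 9.3.1.2, 9.7.3.4 and the matching text at the front of the protocol and in the abstract, extend the pregnancy-outcome population to exposed participants who are pregnant at enrolment or conceive while enrolled. Report the two routes separately, because part of the course of a pregnancy present at entry may already be known.
- **Outcome collection.** Align the sentence in 11.1.3.1 that ties outcome collection to pregnancy during enrolment with the statement in the same section that all pregnancies are collected.
- **Incidence.** In 9.7.3.4, limit incidence to pregnancies with an estimated conception date after enrolment.
- **Exposure wording.** Reconcile the exception in 9.2.1.2 and the abstract with the definition of an exposed pregnancy in 9.7.3.4, including how pregnancy is dated.

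The cost is minor rewording in several places. No new assessment is needed, since the data are already to be collected. The drawback is that the incidence may rest on fewer pregnancies.

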## 9.2.2 Palovarotene-unexposed Cohort

#### 9.2.2.1 Inclusion Criteria

To be included in the palovarotene-unexposed cohort, the participants should fulfil all the following inclusion criteria:

- (1) Paediatric (8 years to less than 18 years of age for girls and 10 years to less than 18 years of age for boys) and adult participants with FOP untreated with palovarotene;
- (2) Signed informed consent as per local regulations must be obtained and maintained. Consent/assent from the participant should be obtained as appropriate before any registry study data collection is conducted. If applicable, parents or legally authorised representatives must give signed informed consent.

#### 9.2.2.2 Exclusion Criteria

Participants will not be included in the palovarotene-unexposed cohort if:

- (1) Currently participating in any interventional clinical trial;
- (2) Previously received palovarotene, other synthetic oral retinoids, or any disease modifying therapy for the reduction of heterotopic ossification.

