**PAGE 40 OF 287** 

- a Follow-up Visits are recommended every 6 months, or as per local label.
- b If participant <18 years (or the legal age of consent in the jurisdiction in which the study is taking place), assent and parent or legally authorised representative consent will also be required.
- c This includes a general assessment, dermatologic, lymph nodes, HEENT, chest, cardiac, abdomen, limb/extremities, musculoskeletal, neurologic and other.
- d Not expected in the context of a telephone/video visit.
- e Collected for growing children. Assessment as per local label.
- f Linear height within 6 to 12 months prior to and at the Baseline Visit.
- g Vital signs to be collected are respiratory rate, blood pressure and heart rate.
- h Participants will be assessed for child-bearing status and pregnancy prevention measures. As per local label, pregnancy testing is carried out with a confirmation of absence of pregnancy monthly if the participant receives palovarotene and one month after stopping. These conditions also concern participants who are not currently sexually active unless the prescriber considers that there are compelling reasons to indicate that there is no risk of pregnancy.
- i This includes a period of two months prior to the signed informed consent date.
- i Not applicable for pregnant participants.
- k Spirometry obtains the lung function parameters of observed and % predicted FVC and FEV1 and the absolute and % predicted FEV1/FVC ratio. The DLCO test obtains observed and % predicted DLCO which provides information on the efficiency of gas transfer from alveolar air into the bloodstream.
- 1 This includes number of flare-ups over the past 12 months before the signed informed consent date.
- m Spinal health assessment to be performed using radiological imaging (e.g. CT, X-ray, scintigraphy, etc).
- n AE, SAE, Special Situation and AESI collection begins once the informed consent has been signed.
- o Paper-based patient-reported questionnaires.

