# For exposed naïve participants (Table 2)

- Baseline demographics;
- Physical examination including a general assessment as well as dermatologic, lymph nodes, head, eyes, ears, nose and throat (HEENT), chest, cardiac, abdomen, limb/extremities, musculoskeletal, neurologic and other assessments (as per routine clinical care);
- Medical or surgical history (12 months before the Baseline Visit);
- FOP history (date of symptom onset, date of diagnosis by a physician, method of diagnosis, date of genetic test if performed and type of FOP genetic variant);
- Growth status assessment for growing children (bone age, knee height and epiphyseal status assessment);
- Tanner staging for growing children;
- Linear height and weight (linear height within 6 to 12 months prior to the Baseline Visit will also be collected);
- Vital signs (respiratory rate, blood pressure and heart rate);
- Pregnancy test (as per local label, participants are assessed for child-bearing status and pregnancy prevention measures. These conditions also concern participants who are not currently sexually active unless the prescriber considers that there are compelling reasons to indicate that there is no risk of pregnancy);
- Prior (two months before the Baseline Visit) and concomitant medications;
- Concomitant surgery and non-drug therapies;
- Prior use of palovarotene (investigational product);
- Marketed palovarotene dose for chronic and flare-up treatment;
- Spirometry and DLCO test;
- CAJIS for FOP;

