# 9.2.8 Registry Study Discontinuation/Withdrawal

The participant can withdraw (or be withdrawn if the subject is a child upon legal representative's decision) from the FOPal registry study at any time. The date and primary reason for withdrawal should be recorded in the eCRF as well as whether the participant stopped or not palovarotene for exposed participants.

Should the participant withdraw from the study, no further data will be collected, nevertheless, data collected up to the time of the withdrawal will be kept for analysis, safety and integrity of study results.

The participant will be withdrawn from the FOPal registry study if:

- The participant enrols in any interventional clinical trial for FOP, or,
- For exposed participants: the participant is no longer receiving palovarotene (except if palovarotene is discontinued due to a safety concern or pregnancy, in such cases the participant will be monitored for safety, see Section 11.4 for follow-up of AEs and Section 11.1.3.1 for follow-up of pregnancies).
- For unexposed participants: the participant becomes pregnant or starts a treatment for FOP other than palovarotene. In case the participant starts palovarotene, they should have the option to remain in the registry. Previously unexposed participants starting palovarotene and remaining in the registry will follow the exposed naïve participants schedule (Table 2) from the first marketed palovarotene intake.

Investigators, participants or/and parents may decide to stop the participation in the FOPal registry study at any time without consequences on the normal participant clinical care.

PAGE 50 OF 287

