# Comparison of key safety outcomes between the Safety Exposed and the Safety Unexposed Populations

The key secondary endpoints that will be descriptively compared between exposed and unexposed participants with FOP in the FOPal registry, include: 1) Annualised frequency of flare-ups categorised by overall occurrence; 2) Annualised linear height velocity and height z-scores until skeletal maturity or final adult height is reached; knee height may also be evaluated depending on data availability, and 3) Annualised frequency and descriptive characteristics of bone fractures, categorised by overall occurrence and location.

The index date (Day 1) corresponds to the initial administration of marketed palovarotene for the exposed participants (naïve and non-naïve), and to the ICF signed date for unexposed participants.

Participants in the Safety Unexposed Population will be followed from their index date until data extraction at the end of FOPal registry, or until start date of palovarotene, or any investigational or commercialised FOP first treatment intake, whichever comes first.

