# Matching of Exposed Participants to Unexposed Participants

The Safety Exposed Population will be matched with the Safety Unexposed Population. To minimise potential selection bias resulting from differences between these two populations, the PS method will be employed with the Inverse Probability of Treatment Weighting (IPTW) method, ensuring that both populations are balanced concerning crucial baseline variables.

For constructing the PS model, logistic regression will be used. This model will encompass essential baseline covariates (at index date), including age, gender, time since the last flare-up, and the total CAJIS score. Additional covariates may be included if deemed necessary. Balance diagnostics before and after applying weights will be reviewed to assess if there is any important residual imbalance. Standardised mean differences (SMDs) will be used to compare baseline covariates and estimated propensity scores between exposed and unexposed populations. SMDs greater than 0.1 for individual covariates on the weighted sample signify residual imbalance that may lead to biased results. A density plot of the estimated propensity scores by population will be generated to visually inspect the amount of overlap between the populations. A box plot of the propensity score weights for the unexposed population will also be generated to visually inspect for highly influential observations.

Other methods will be detailed in the SAP if needed.

The number and proportion of missing data for each baseline covariate to be included in the propensity score model will be reported for exposed and unexposed populations. The analysis

PAGE 66 OF 287

methods will proceed as a complete case analysis if, and only if, the proportion of participants in the unexposed participants with at least one missing value among variables required for the model is less than 5%. Otherwise, in addition to the complete case analysis, multiple imputation will be used as a sensitivity analysis to handle missing data. The methods to evaluate the effect of missingness and to handle missing data will be detailed in the SAP.

For participants who start palovarotene (or any investigational or commercialised FOP treatment) after being in the unexposed population, only their data until palovarotene intake with a minimum of 6 months of data collected will be included in the analysis.

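### The exposed-versus-unexposed safety comparison controls other anti-HO therapy and oral retinoids in the unexposed arm only

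*Protocol*

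**What the plan says.** **Entry.** Protocol Section 9.2.2.2 keeps out of the unexposed cohort anyone who has "Previously received palovarotene, other synthetic oral retinoids, or any disease modifying therapy for the reduction of heterotopic ossification". No look-back limit is given. Section 9.2.1.2 gives the exposed cohort two exclusions only: current participation in an interventional trial, and a label contraindication (with an exception for some pregnant participants). The abstract repeats both lists, so the difference is not a slip of transcription.

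**Follow-up.** Section 9.2.8 withdraws participants in either cohort who enter an interventional FOP trial. Unexposed participants are also withdrawn if they start an FOP treatment other than palovarotene. For exposed participants the further ground is that "the participant is no longer receiving palovarotene (except if palovarotene is discontinued due to a safety concern or pregnancy" (with safety follow-up in those cases). For the comparison itself, Section 9.7.3.4 states: "Participants in the Safety Unexposed Population will be followed from their index date until data extraction at the end of FOPal registry", or until palovarotene or a first investigational or commercialised FOP treatment is started, if earlier. It states no matching end point for exposed participants.

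**Populations and weighting.** Section 9.7.1 defines the Safety Exposed Population as "all enrolled participants who have taken at least one dose of marketed palovarotene at any time" before consent or during the study. Section 9.7.3.4 then says "The Safety Exposed Population will be matched with the Safety Unexposed Population", by inverse probability weighting on age, gender, time since last flare-up and total CAJIS score. Further covariates are optional.

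**Data collected.** For exposed naïve participants, the Table 2 note on prior medication reads "This includes a period of two months prior to the signed informed consent date". For non-naïve participants the window opens two months before the first marketed intake and runs to the Baseline Visit (Section 9.2.7.1). FOP history in Section 9.3.2.1 covers onset, diagnosis and genetics, not treatment. One item in Tables 2 and 3 does reach further back: "Prior use of palovarotene (investigational product").

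**The concern.** By writing the unexposed exclusion, the plan treats earlier retinoid or anti-HO therapy as capable of affecting the outcomes. It then removes that influence from one side of a contrast and leaves it on the other.

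Any lasting effect of such drugs on flare-ups, growth or fractures, and any effect of an FOP treatment added to palovarotene, stays in the exposed estimate and would be read as part of the palovarotene contrast. Comparing these outcomes is a stated aim in Section 8.1, and it is the only place where the registry sets exposed participants against controls.

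**Working it through.** The plan gives no figure to reproduce: the 67 and 33 enrolment minima come without an event rate, standard deviation or effect size. The check sets the rules side by side, asks whether weighting can repair the difference, and then illustrates the size.

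**1. Rules side by side**

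| | Exposed | Unexposed |
|---|---|---|
| Earlier other synthetic oral retinoid or anti-HO therapy | Allowed | Excluded, lifetime |
| Earlier investigational palovarotene | Allowed and recorded | Excluded by definition of the cohort |
| Enters an interventional FOP trial | Withdrawn | Withdrawn |
| Starts a non-trial FOP treatment other than palovarotene | No stop while on palovarotene | Withdrawn, and follow-up ended in the comparison |

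The second row needs care. Barring earlier palovarotene from the unexposed cohort is simply what unexposed means. What matters is that exposed participants may have had palovarotene before the Day 1 index date, which is the first marketed dose, and no analysis use of that item is stated.

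**2. Can weighting repair it?** Let Z = 1 mark earlier therapy. By design no unexposed participant has Z = 1, so P(exposed | Z = 1) = 1. No control exists in that stratum to be weighted up, and a logistic model containing Z would be driven to a fitted probability of 1 for those people. The permission to add covariates therefore does not help; restricting the comparison does. The planned balance diagnostics cannot show the problem either while Z is unrecorded.

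**3. Can it be left to the analysis plan?** In part.
- Therapy added during follow-up: yes. Section 9.3.2.2 records concomitant medication with start and end dates.
- Earlier investigational palovarotene: yes, through its own item.
- Lifetime use of other retinoids or anti-HO therapy: no. Use that ended before the two-month window has no designated field, and medical history covers 12 months and leaves out FOP-related history.

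**4. Illustrative size.** Suppose palovarotene has no effect, a share f of exposed participants had earlier or added therapy, and that therapy multiplies their event rate by r throughout follow-up. The unexposed share is 0. The spurious rate ratio is then 1 + f(r − 1).

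| f (assumed) | r = 0.5 | r = 2.0 |
|---|---|---|
| 10% | 1 + 0.10 × (−0.5) = 0.95 | 1 + 0.10 × 1 = 1.10 |
| 25% | 0.875 | 1.25 |
| 50% | 0.75 | 1.50 |

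The documents give neither f nor r. The one related count is in Section 7.3.1: 139 people in the target age range had already received palovarotene in the clinical studies, 139/67 = 2.1 times the exposed minimum. Earlier investigational use could therefore be common in the registry, but how many of these people will enrol is not stated.

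**The case against.** The strongest reply is that a never-treated comparator beside an all-comers safety cohort is a defensible choice, that the comparison is descriptive with intervals and no testing, and that the likely bias is small against sampling error. With 67 and 33 participants, the unweighted 95% half-width for a difference in means is 1.96 × √(1/67 + 1/33) = 0.42 standard deviations. If the standard deviation equals the mean (an assumption), that is about 42% of the mean, well beyond a 5% to 10% shift. The protocol also names no other marketed anti-HO drug and describes earlier care as symptom management and flare-up prevention.

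This stands as a limit on importance. It does not remove the asymmetry: the shift is systematic, the interval does not reflect it, and the plan itself thought such therapy relevant enough to exclude from the controls.

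Three stronger readings are tempting, and the documents do not support them.

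- *Exposed participants could come straight from another trial while controls could not.* The trial criterion has the same wording in both cohorts. Any difference arises from the prior-therapy exclusion.
- *Therapy added during follow-up cannot be handled.* Exposed participants who enter an FOP trial are withdrawn, as are those who stop palovarotene other than for safety or pregnancy. What remains is a non-trial treatment added to palovarotene or started after a safety stop, and dated concomitant medication would identify it. The data exist while the patient is followed; the rule is missing.
- *Controls who could never have received palovarotene break the comparison.* Only the exposed criteria say "Palovarotene is contraindicated as per the locally approved label", so a reader might infer a second lack of overlap. The label is not among the documents. The examples named are pregnancy and breastfeeding, both temporary. Section 9.2.1.2 admits some pregnant participants to the exposed cohort, and Section 9.2.8 withdraws unexposed participants who become pregnant. That is too thin to build on.

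**Conclusion.** The point holds within limits. In the Section 9.7.3.4 comparison, other anti-HO therapy and synthetic oral retinoids are controlled on the unexposed side at entry and during follow-up, and on the exposed side at neither stage beyond the common trial rule. Weighting cannot correct the entry difference, and for lifetime use of other agents the data needed to restrict the comparison are not collected.

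The size and direction of the bias are unknown. The range of 0.95 to 1.10 at a 10% share, widening to 0.75 to 1.50 at 50%, rests wholly on assumed prevalence and rate ratios, and on past therapy acting throughout follow-up. What is affected is the interpretation of one descriptive secondary comparison. The primary objective concerns exposed participants only and does not change. The reason to act now is practical: enrolment may run for up to 10 years, and a history not asked for at baseline may not be recoverable later.

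**What to change.** Leave cohort entry, treatment, registry participation and the primary analysis as they are. For the Section 9.7.3.4 comparison only:

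1. State an end of follow-up for exposed participants at first intake of any other investigational or commercialised FOP treatment, in the same words as the unexposed rule. Use the concomitant-medication dates already collected, including the retrospective period for non-naïve participants. This ends time at risk in the analysis; it does not affect care or withdrawal.
2. Add one baseline eCRF item for exposed participants: lifetime use of other synthetic oral retinoids or anti-HO disease-modifying therapy, with drug and last date.
3. Report a sensitivity analysis that leaves out exposed participants with such use or with earlier investigational palovarotene.

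The cost is one eCRF item, a few sentences in Section 9.7.3.4, somewhat less person-time in a secondary comparison, and a smaller exposed group in the sensitivity analysis. If earlier investigational use proves common, that analysis will be imprecise, so the number left out should be reported beside it.
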